Role of Virtual Reality (VR) in Decreasing Pain and Anxiety in Patients with Sickle Cell Disease (SCD) and Cancer

Protocol Summary

NCT03387033

1. Protocol Title: Role of Virtual Reality (VR) in Decreasing Pain and Anxiety in Patients with Sickle Cell Disease (SCD), Cancer, and Bone Marrow Transplant (BMT) Patients

2. Purpose of the Study: We propose implementing a feasibility study of the use of VR in patients with SCD, cancer, and bone marrow transplant patients. We plan to assess pain as well as anxiety and depressive symptoms prior to the session as well as following the session for inpatients and outpatients with SCD, malignancy, and patients undergoing/who underwent BMT. The sessions will include a ten-minute relaxation response introductory narrative segment (deep breathing and mindfulness) followed by a ten-minute narrated and immersive VR. **We hypothesize the use of VR will not only be feasible, but will also decrease pain, anxiety and depressive symptoms in hospitalized patients and outpatients with SCD, cancer, and BMT patients.**

3. Background & Significance: Pain, anxiety and depression contribute significantly to health care visits and subsequently contribute substantially to the cost of the healthcare system. In 2009-2010, visits related to mental health as primary concern accounted for over 63 million visits in the outpatient setting.¹ Patients with sickle cell disease (SCD) often have complicated courses while hospitalized and often deal with pain, anxiety, and depression. SCD is a chronic blood disorder with patients typically experiencing daily pain with frequent hospital admissions for worsened acute pain. Cancer and BMT patients also commonly deal with pain related to primary malignancy, side effects of chemotherapy, transplant complications, etc. They may also have symptoms of anxiety and depression in the setting of chronic illness.

Therapy is often focused on pharmacologic therapies, which are often not adequate and have side effects such as sedation. An increasing focus has therefore been placed on non-pharmacologic therapies. The scope of non-pharmacologic interventions has developed over the last several years with innovations in technology. Advances in the field of technology provide potential avenues for innovative and improved care models for our patients. Virtual reality (VR) has been recently utilized to improve anxiety and pain in a variety of patient populations including children undergoing elective surgery² and children experiencing intravenous cannulation in the Emergency Department.³ Patients with SCD, cancer, and BMT patients are groups of patients that can benefit from VR as part of their care as VR has shown effectiveness in providing remarkable non-pharmacologic therapy.

4. Design & Procedures: We will perform a feasibility and pilot study evaluating relaxation response (narration leading through deep-breathing, mindfulness, and other relaxation techniques) followed by VR in patients with sickle cell disease (SCD), cancer, and BMT patients. The VR headset (Dynamic Virtual Viewer or similar device) used will be compatible with an iPhone application titled Provata VR. The devices are provided by the study personnel. The virtual reality headset is commercially available. Different VR headsets have been used in prior studies, some compatible with computer programs and other compatible with a Samsung

Role of Virtual Reality (VR) in Decreasing Pain and Anxiety in Patients with Sickle Cell Disease (SCD) and Cancer

Protocol Summary

device. The VR session will be narrated by [name], and the image through the Provata VR mobile application has been chosen by the study team.

They will then listen to a ten-minute relaxation response recording by [name] on an iPhone. Following this, the image on Provata VR will be opened, the narration of the VR image by [name] will be started on the iPhone, and the VR headset secured. The patient should be sitting or lying down for the VR portion of the session to decrease the risk of injury. The audio narration will play while the patient is viewing the VR image. The study team will be supervising the patient while the headset is in use. No patient data will be stored on the iPhone, it simply allows the patient to view the VR image through the VR headset with narration by [name]. During the entire session, patients will also wear an Apple iWatch to passively record objective data such as heart rate through the Health app. For 30 minutes prior to and following the session, patients will also wear the Apple iWatch.

The patients will first be provided a consent form and consented. They will have the opportunity to ask questions prior to and following consent. They will subsequently fill out a GAD-7 (Generalized Anxiety Disorder) and PHQ-9 (Patient Health Questionnaire) form. They will complete the session described above. Patients will also provide an initial pain score and answer questions through the TRU-Pain app. Following this, patients will complete another GAD-7, PHQ-9, pain score, Presence Questionnaire, Feasibility Questionnaire, Patient's Global Impression of Change (PGIC) form, and answer questions in the TRU-Pain app. Patients will then be able to ask questions/provide further feedback.

5. Selection of Subjects: A total of 60 subjects, including inpatients and outpatients with SCD, malignancy, and patients undergoing/who underwent BMT. Approximately half of these patients will be inpatient and half will be outpatient. These patients must have a diagnosis of chronic or acute pain (current pain or baseline pain score >0) or have at least one symptom of anxiety or depression as measured by the GAD-7 or PHQ-9 questionnaires (positive response to any question).

6. Subject Recruitment & Compensation: Admitted patients with SCD, malignancy, or BMT patients for malignant or non-malignant disorders on the Hematology/Oncology and Bone Marrow Transplant Services in addition to outpatients with SCD, malignancy, and BMT patients for malignant and non-malignant reasons will be eligible for participation. This study will be known to Hematology, Oncology, and Bone Marrow Transplant providers. Personnel from this study will present to clinic and assess with other providers if certain patients being seen that day would fit the inclusion criteria for the study. The patient's primary care team alerts study personnel of their possible eligibility and interest. No further recruitment will likely be needed. Patients will not be compensated and the study/session involves minimal risk to the patient. As per Duke University protocol, there will be no "cold contact" whereby a patient is approached by the research team without the study having been introduced by a person known to the patient before.

Role of Virtual Reality (VR) in Decreasing Pain and Anxiety in Patients with Sickle Cell Disease (SCD) and Cancer

Protocol Summary

7. Consent Process: Risks/benefits will be explained to the patient as well as their parent(s)/guardian(s) as part of the consent process and they will have the ability to review the consent form. As much time as needed will be given for the adult patients, and the minor patients along with their parents, to make an informed decision. All questions and concerns will be answered to the potential subject's satisfaction and will verbalize understanding prior to signing the consent form.

8. Subject's Capacity to Give Legally Effective Consent: Individuals (or parents of minors) that cannot read and/or understand the requirements, and "no guarantee" of benefit of the study will not be eligible for participation. The protocol of this study targets populations that are unlikely to have impaired decisional capacity. If there is a concern for impaired capacity during the clinical interview, that patient will be excluded from the study. Parents of minors are expected to provide consent, but may be excluded from providing consent and thereby the patient excluded from the study if the parent is unable to read, cannot speak or understand English, or has impaired capacity to give legally effective consent.

9. Study Interventions: A 30 minute session with ten-minute relaxation response and ten-minute narrated VR with surveys before and after session. Patients will wear an Apple iWatch to passively record objective data. Patients will also wear an Apple iWatch for 30 minutes prior to and 30 minutes following session to record objective data passively.

10. Risk/Benefit Assessment: This study involves minimal risk given the imagery/narrative used will likely either be seen in a neutral or positive light. Loss of PHI and breach of patient confidentiality are possible risks. The potential benefits include improvement in anxiety and/or depressive symptoms. The results of this study will be critical as feasibility and pilot analysis to use for power analysis and future grant submissions with additional collaborators. Minimal risk to using TRU-Pain app given the data gathered is de-identified.

11. Costs to the Subject: The subjects will not have any costs associated with the study other than the utilization of approximately 90 minutes of their time for the session.
Routine medical care will be charged to the subject or their insurance company.

12. Data Analysis & Statistical Considerations: The endpoints of the study are feasibility of 30-minute VR sessions and change in pain, GAD-7, and PHQ-9 scores. Study personnel with assistance of Duke statistician if needed will analyze the data to determine if any significant change in GAD-7 and PHQ-9 was noted in any group with the study intervention. This data/outcome of the study will be used to power future studies.

A sample size of approximately 60 is appropriate given this is a feasibility study. Within 1 year, these patients hopefully will be reached.

13. Data & Safety Monitoring: The data will be obtained with the use of Duke Box to maximize the protection of each patient's data. Objective data collected on the Apple iWatch

Role of Virtual Reality (VR) in Decreasing Pain and Anxiety in Patients with Sickle Cell Disease (SCD) and Cancer

Protocol Summary

will be uploaded to Citrix Sharefile via the TRU-Pain HKO app and will subsequently be transferred to Duke Box. Data gathered from the TRU-Pain app will be sent to Citrix Sharefile and Duke Box as well. There will not be an independent data monitoring committee for this study. The PI will review and sign off on all adverse events and any problems. These will be reported to the IRB in accordance with HRPP policies.

14. Privacy, Data Storage & Confidentiality: Patient privacy will be maximized by allowing only the patient, their parent(s)/guardian(s) and the study personnel during the session. Data will be stored with the use of Duke Box and Citrix Sharefile to maximize patient confidentiality. All subjects are assigned a unique study number when enrolling. Study staff will follow all HIPPA guidelines when enrolling and explaining the study to subjects and their parents. All doors will be kept closed and all human traffic into the area kept to a minimum. All study related documents are kept in a locked file in the research offices in [name]. No PHI will leave DUHS. All computer databases are password protected. Only staff involved with the study have access to the study data. All study related documents will be kept per requirements for 6 years after the close of the study.

Bibliography

¹ National Center for Health Statistics: Mental Health. CDC.
<https://www.cdc.gov/nchs/fastats/mental-health.htm>

² Chow, C.H., et. al. Systematic Review: Audiovisual Interventions for Reducing Preoperative Anxiety in Children Undergoing Elective Surgery. *Journal of Pediatric Psychology*. 2016;41(2):182-203.

³ Miller, K., et. al. A Prospective Randomized Controlled Trial of Nonpharmacological Pain Management During Intravenous Cannulation in a Pediatric Emergency Department. *Pediatric Emergency Care*. 2016;32(7):444-451.

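### The title and efficacy hypothesis credit VR with symptom reduction, but a single-arm relaxation-plus-VR session rated only before and after can show only uncontrolled change

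*Combined protocol and SAP*

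**What the plan says.** The title (section 1) reads "Role of Virtual Reality (VR) in Decreasing Pain and Anxiety". The hypothesis in section 2 has two parts: "We hypothesize the use of VR will not only be feasible, but will also decrease pain, anxiety and depressive symptoms". Neither names the relaxation component. Section 3 does not mention relaxation either; it says that these patients "can benefit from VR as part of their care as VR has shown effectiveness in providing remarkable non-pharmacologic therapy".

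The intervention itself has two components. Section 2: "The sessions will include a ten-minute relaxation response introductory narrative segment (deep breathing and mindfulness) followed by a ten-minute narrated and immersive VR". Section 4 opens with "We will perform a feasibility and pilot study evaluating relaxation response" and goes on to say that VR follows it; its procedure then has patients hear the recording ("They will then listen to a ten-minute relaxation response recording") before the headset is fitted. Section 9 gives the same content: "A 30 minute session with ten-minute relaxation response and ten-minute narrated VR with surveys before and after session".

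On timing, section 2 says "We plan to assess pain as well as anxiety and depressive symptoms prior to the session as well as following the session". Section 4 lists one set of questionnaires and a pain score at the start and one set at the end. During the session it describes only passive watch data such as heart rate. No control arm, randomisation or crossover is described.

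Section 12 makes change in pain, GAD-7 and PHQ-9 an endpoint alongside feasibility, and looks for significant GAD-7 and PHQ-9 change in any group with the study intervention. Sections 10 and 12 both say that the results will be used for power calculations.

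**The concern.** The efficacy part of the hypothesis is a causal statement about one component. The data come from patients who all receive two components in a fixed order, with nothing to compare them with. The first component, deep breathing and mindfulness, is itself intended to relax patients, so it is a plausible cause of the same improvement. If scores fall, the plan as written invites the conclusion that VR reduced pain, anxiety and depressive symptoms, and following the plan exactly would not make that conclusion sound.

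A second consequence concerns later use. The protocol intends the results to power future studies but does not say which quantities will be carried forward. Without a limit, the observed mean change could be taken as the effect expected between randomised groups. Uncontrolled change is not a safe value for that, whether the later study tests VR or the whole session.

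**Working it through.** The plan gives no figure to reproduce. The sample of about 60 is justified only by the study being a feasibility study, with no alpha, power, effect size or SD. The check is therefore one of identifiability.

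**Inputs.** Every patient receives relaxation and then VR (sections 2, 4, 9). Symptoms are rated once before and once after (sections 2, 4, 9). I take the initial pain score in section 4 to be pre-session, as section 2 states. Total 60 patients (section 5).

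**Step 1: can VR be separated?** Write the mean score as b0 + b1·(after) + b2·(relaxation received) + b3·(VR received). Each patient contributes two rows:

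- before: (1, 0, 0, 0)
- after: (1, 1, 1, 1)

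Mean change = b1 + b2 + b3. That is one estimable contrast for three unknowns. Stacking these rows for 60 patients gives 120 rows, and the matrix has rank 2 for 4 columns. More patients repeat the same two rows, so the rank stays at 2 at any sample size.

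**Step 2: can the session as a whole be separated from everything else?** Merge the two components into one session term, bS = b2 + b3. The rows become (1, 0, 0) and (1, 1, 1), with rank 2 for 3 columns, and mean change = b1 + bS. The session effect is still tied to b1, which stands for whatever else accompanies the second rating: passage of time, concurrent care, expectancy and regression to the mean.

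**Step 3: do the groups in section 12 help?** No. Whether split by diagnosis or by inpatient and outpatient status, all patients have the same session, so each group has the same two rows. The groups are not treatment arms.

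**Step 4: is regression to the mean relevant?** Section 5 admits patients with pain (current, or a baseline score above 0) or with at least one positive GAD-7 or PHQ-9 answer. Selection on having a symptom tends to make later scores on the qualifying measure look better. The threshold is low, so this may be small; the documents give nothing from which to size it.

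**Step 5: does anything else collected separate the components?** Heart rate is recorded throughout and the Presence Questionnaire concerns the VR experience, but neither is a pain, GAD-7 or PHQ-9 rating, and section 12 plans no analysis of them.

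**The case against.** The strongest reply is that this is mainly labelling. The hypothesis follows directly after the sentence defining the session, where relaxation is an introductory segment, so VR can be read as shorthand for the whole session. Section 12 supports this by naming the feasibility endpoint after VR sessions of 30 minutes, the session length in section 9. Section 4 states openly that the combination is being evaluated, and section 12 refers to the study intervention. A single-arm pilot is a legitimate choice, and nobody reading the protocol would be misled about what patients receive.

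Most of that stands, and it is why the point is minor. It does not remove the point, for two reasons. Section 4 elsewhere treats VR as one portion of the session, so the shorthand is not used consistently. More importantly, reading VR as the whole session disposes of step 1 but not step 2: a claim that the session decreases symptoms still lacks a control.

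A reader might go further and infer that a later trial of VR against relaxation alone would be underpowered if sized on this change. The documents do not support that: they mention no such trial and give no share of the change due to VR. Nor can a share be inferred from the two segments being equally long, because duration says nothing about contribution to effect.

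**Conclusion.** The point holds as a minor one. The title and the efficacy part of the hypothesis claim more than the design can deliver. What the study can report is uncontrolled pre-to-post change over a relaxation-plus-VR session, attributable neither to VR nor causally to the session. The rank result does not depend on effect size, SD or sample size. It rests only on all patients receiving the same session and on there being no symptom rating other than before and after, both of which the text supports. How much of any observed change would be due to something other than VR cannot be stated from the documents.

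Two broader conclusions are not supported. The feasibility aim is unaffected and can be answered as designed. And the protocol does not hide the relaxation component; the mismatch is between its own description of the session and its title and efficacy wording.

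**What to change.** 1. Align the title and the efficacy hypothesis in section 2 with section 4, naming relaxation response followed by VR, and word the efficacy aim as uncontrolled pre-to-post change in pain, GAD-7 and PHQ-9.
2. State in section 12 that the change scores do not estimate a causal effect of VR or of the session.
3. State in section 12 that, for planning later studies, this study will supply feasibility rates and variability (SDs and pre-post correlation), and that the observed mean change will not be used as the expected between-group effect.

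This is a short wording amendment with no added visits, ratings, arms or patients. The price is giving up the VR-specific efficacy claim. I would not add a pain rating between the two segments: with fixed order, possible carry-over and no control, it still would not allow attribution to VR, and it could interrupt the relaxed state.

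### Pain is rated only once before the session and nothing is rated in the 30-minute watch lead-in, so settling that would have happened anyway cannot be told apart from a session effect

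*Combined protocol and SAP*

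**What the plan says.** Entry (section 5, Selection of Subjects) is by one of two routes. The first is pain: "These patients must have a diagnosis of chronic or acute pain (current pain or baseline pain score >0"). The second is "at least one symptom of anxiety or depression as measured by the GAD-7 or PHQ-9 questionnaires (positive response to any question"). About half of the 60 patients are to be inpatients.

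Section 4 gives one set of ratings on each side of the session. After consent: "They will subsequently fill out a GAD-7 (Generalized Anxiety Disorder) and PHQ-9 (Patient Health Questionnaire) form". For pain: "Patients will also provide an initial pain score and answer questions through the TRU-Pain app". After the session: "Following this, patients will complete another GAD-7, PHQ-9, pain score, Presence Questionnaire, Feasibility Questionnaire", among other forms.

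The watch is worn during the session and for half an hour on either side: "For 30 minutes prior to and following the session, patients will also wear the Apple iWatch". Section 9 (Study Interventions) describes these periods in the same way: "Patients will also wear an Apple iWatch for 30 minutes prior to and 30 minutes following session to record objective data passively". Neither section attaches a symptom rating to the lead-in or says whether the initial pain score comes at its start or its end.

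No control group, waiting period or adjustment for time is described. Section 2 hypothesises that VR will lower pain, anxiety and depressive symptoms. Section 12 makes change in pain, GAD-7 and PHQ-9 endpoints alongside feasibility, looks for significant change with the intervention in GAD-7 and PHQ-9 (pain is not named in that sentence), and intends the results to power later studies.

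**The concern.** A single before/after difference is the sum of what the session does and what would have happened over the same minutes without it. In this population the second part need not be zero. Section 3 says of sickle cell disease: "SCD is a chronic blood disorder with patients typically experiencing daily pain with frequent hospital admissions for worsened acute pain". Pain that has recently worsened may ease over an hour or two, under routine care or by itself. Patients admitted on a positive symptom score also tend to score somewhat lower next time through regression to the mean.

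The plan already holds each patient for 30 minutes without the session, and that is where a pre-existing trend could be seen. With one pre-session score there is no trend to look at. If the initial score is taken when the watch goes on, the half hour of lead-in is itself added to the change credited to the session.

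At stake are the efficacy reading of the pilot and the effect sizes it hands on. An effect inflated by settling would leave the next trial too small. The feasibility endpoint is not touched.

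**Working it through.** **Figures in the plan.** There is no sample size calculation to reproduce: section 12 justifies about 60 patients only by the feasibility purpose and gives no alpha, power, effect size or SD. The one time figure that can be checked agrees: 30 (lead-in) + 30 (session) + 30 (after) = 90 minutes, as in section 11.

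**Inputs.** From the documents: n = 60; the entry rule; one rating before and one after. Assumed, because the documents do not give them: a 0–10 pain scale, two-sided 5% testing, a paired comparison, and the means, SDs and correlations stated below. No true session effect is assumed throughout. The nominal chance of a significant decrease is then 2.5%.

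**1. Regression to the mean from the written rule.** Simulate rounded 0–10 ratings with mean 3.5, SD 2.8 and between-rating correlation r; keep patients whose first rating is at least 1; take the mean fall to the second rating; obtain the chance of significance from the non-central t with 59 df.

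| r | mean fall | SD of change | chance of significant decrease |
|---|---|---|---|
| 0.9 | 0.07 | 1.28 | 6% |
| 0.8 | 0.12 | 1.73 | 8% |
| 0.7 | 0.18 | 2.06 | 10% |

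This ignores the questionnaire route, which admits patients with pain 0, whose score can only stay or rise. If half of the pain-0 patients enter that way, the fall is about 0.03 to 0.08 points (chance 4% to 5%); if 80% do, 0.01 to 0.03 (about 3%).

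A closed form gives the same picture: fall = (1 − r) × SD × φ(a)/(1 − Φ(a)), with a = −mean/SD. At mean 4, SD 2.5 and r = 0.8 it is 0.06 points. Over means 2 to 5, SD 2 to 3 and r 0.6 to 0.9 it runs from 0.00 to 0.51.

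**2. Real settling.** Take a 0.5-point drift and SD of change 2. Standard error = 2/√60 = 0.258; non-centrality = 0.5/0.258 = 1.94; chance of a significant decrease = 48%.

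More generally, SD of change = SD × √(2(1 − r)). With SD 2.5 and r = 0.8 this is 1.58; 0.5/(1.58/√60) = 2.45; Φ(2.45 − 1.96) = 0.69. Over SD 2 to 3 and r 0.6 to 0.9 (normal approximation):

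| drift between ratings | chance of significant decrease |
|---|---|
| 0.25 | 0.11 to 0.58 |
| 0.5 | 0.30 to 0.99 |
| 1.0 | 0.82 to 1.00 |

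**3. What a second pre-session score buys.** Add a third rating to the model in step 1, still selecting on the first.

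- Change from the second score to the post-session score: mean about 0, chance of a significant result 2.5% each way. The regression has already occurred during the lead-in.
- Session change minus lead-in change: mean fall of −0.07 to −0.18 points with entry at pain 1 or more, so an inert session looks slightly harmful. Subtracting the lead-in puts the regression back with the opposite sign.
- Precision: the SD of the net change is SD × √(6(1 − r)), which is √3 = 1.73 times that of the simple change. With SD 2.5 and r = 0.8, the change detectable with 80% power at n = 60 goes from 0.57 to 0.99 points.

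A constant drift cancels in the net change; a drift that slows is only partly removed. The second baseline removes the lead-in's share of the drift but not what happens during the session.

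**The case against.** The strongest reply is that this is a feasibility pilot, that its written threshold selects hardly at all, and that the documents show no drift. Section 12's significance sentence does not even name pain.

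Much of this stands. Feasibility is unaffected, the entry rule produces little regression, and the 0.5-point drift is an assumption. The section 3 sentence on sickle cell disease also speaks of daily pain, which tempers the expectation of rapid settling. But pain change is an endpoint, the hypothesis is directional, and the results are meant for power calculations, so the size of the change will be used.

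Three stronger readings are tempting and are not supported.

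- A reader might infer that selection makes a false positive likely. If only patients with pain of 4 or more were referred, the model in step 1 would give falls of 0.25 to 0.69 points and false-positive chances of 32% to 73%. No section states such a cut-off.
- A reader might treat the lead-in as an untreated run-in in patients chosen for symptoms at that moment. Routine care continues (section 11), and the entry wording also covers diagnosed chronic pain with a baseline score above 0, or a single positive questionnaire item.
- A reader might conclude that session-minus-lead-in change should carry the pain conclusion. Step 3 shows why not. Were entry at pain 4 or more, its bias would reach −0.25 to −0.69 points.

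**Conclusion.** The point holds as a design weakness of moderate weight. With one pre-session pain score, no rating in the lead-in and no comparator, the plan cannot show whether pain was already falling, and whatever settling occurs is counted as a session effect.

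The entry rule contributes little: 0.07 to 0.18 points at mean 3.5, SD 2.8 and r 0.7 to 0.9, and less with the questionnaire route. The main exposure is real change over time, including change under routine care. Its size cannot be obtained from the documents; a 0.5-point drift with SD of change 2 would give a 48% chance of a spurious significant decrease at n = 60. These figures rest on the stated assumptions and illustrate sensitivity; they do not estimate bias in this trial. The result that the second baseline is free of regression to the mean further assumes that selection acts on the first score. The documents do not say whether the initial pain score is the one used for eligibility.

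**What to change.** In section 4, record the pain score when the watch is put on and again just before the relaxation recording starts, with the time of each rating. In section 12:

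- Define pain change from the second score, which also settles the undefined timing of the baseline.
- Report the lead-in change beside the session change, with the length of each interval.
- Present session-minus-lead-in change only as a supportive check on drift, not as the basis for the pain conclusion.
- State that, without a control group, a before/after fall in pain, GAD-7 or PHQ-9 cannot be attributed to the session alone, and carry that caution into any use of the estimates for powering. The extra rating covers pain only, so for the two questionnaires this statement is the whole remedy.

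Cost: one extra rating of a few seconds in time the patient already spends wearing the watch, and a few protocol sentences. The reported pain change may come out smaller.

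### No listed measure is described as a present-moment rating of anxiety or mood, and the recall wording of GAD-7 and PHQ-9 is not stated, so their same-visit change may not show the session's immediate effect

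*Combined protocol and SAP*

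**What the plan says.** Section 2 sets the aim: "We plan to assess pain as well as anxiety and depressive symptoms prior to the session as well as following the session". The hypothesis there is that pain, anxiety and depressive symptoms will all fall.

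Section 4 gives the sequence. After consent, "They will subsequently fill out a GAD-7 (Generalized Anxiety Disorder) and PHQ-9 (Patient Health Questionnaire) form". The session follows. Then: "Following this, patients will complete another GAD-7, PHQ-9, pain score, Presence Questionnaire, Feasibility Questionnaire", with the PGIC and a further set of TRU-Pain questions completing the list. For the other ratings at the start, "Patients will also provide an initial pain score and answer questions through the TRU-Pain app". A watch records heart rate throughout.

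Section 9 describes the intervention as "A 30 minute session with ten-minute relaxation response and ten-minute narrated VR with surveys before and after session", and adds: "Patients will also wear an Apple iWatch for 30 minutes prior to and 30 minutes following session to record objective data passively". Section 11 puts the patient's total time at about 90 minutes. No later contact is described.

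Section 12 names feasibility and three change scores (pain, GAD-7, PHQ-9) as endpoints. GAD-7 and PHQ-9 are the only two scores it names when it describes the analysis for significant change. Sections 10 and 12 both say the results will feed the power calculation of later studies.

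Section 5 also uses the two forms for eligibility: "at least one symptom of anxiety or depression as measured by the GAD-7 or PHQ-9 questionnaires". No section gives a recall period for either form, or says that the wording is altered for the second completion.

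**The concern.** The question is what one session does to a patient's anxiety and mood there and then. A form that asks about a past period mostly asks about time before the session, at both completions. A null result could then mean that the session had no effect, or that the form could not register one. A fall could mean relief, or a second rating of much the same past days. The reader could not tell which.

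This matters because two of the three change endpoints rest on these forms, and because their results are meant to inform the size of later trials. An immediate rating that was not taken at the visit cannot be recovered afterwards.

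**Working it through.** The plan has no figure of its own to reproduce here. The sample size of about 60 is justified only by the study being a feasibility study, with no alpha, power, standard deviation or effect size.

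**Step 1: is a present-moment rating of anxiety or mood listed?** Going through the measures in section 4:

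- GAD-7 and PHQ-9: before and after; recall wording not stated.
- Pain score: not a rating of anxiety or mood.
- Presence and Feasibility Questionnaires: listed only after the session; not described as anxiety or mood ratings.
- PGIC: listed only after the session, and not described as specific to anxiety or mood.
- TRU-Pain questions: answered with the initial pain score and again at the end; content not given.
- Heart rate by watch: before, during and after, but an indirect physiological measure.

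None is described as a present-moment rating of anxiety or mood. The TRU-Pain questions could contain one; the document does not say.

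**Step 2: how far apart are the two completions?** No section times the first forms, so this is a range.

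- Lower end: 10 + 10 = 20 minutes, the relaxation and VR segments alone. This applies if the 30-minute session in section 9 includes the surveys. If it does not, the gap is at least 30 minutes.
- Upper end: 30 + 30 + 30 = 90 minutes (watch before, session, watch after). This is inferred. It equals the approximate total in section 11 and leaves no time for the forms themselves.

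**Step 3: how much of the rated period is shared?** The recall period is an assumption, taken as 1, 7 or 14 days (1,440, 10,080 or 20,160 minutes). Shared fraction = 1 − gap / recall period.

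| Assumed recall | Gap 90 min | Gap 30 min | Gap 20 min |
|---|---|---|---|
| 1 day | 1 − 90/1,440 = 93.75% | 1 − 30/1,440 = 97.92% | 1 − 20/1,440 = 98.61% |
| 7 days | 1 − 90/10,080 = 99.11% | 1 − 30/10,080 = 99.70% | 1 − 20/10,080 = 99.80% |
| 14 days | 1 − 90/20,160 = 99.55% | 1 − 30/20,160 = 99.85% | 1 − 20/20,160 = 99.90% |

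**Step 4: does an earlier first form remove the problem?** Suppose the first forms were filled in 24 hours earlier (assumption). The overlap falls to 0% for 1 day, 1 − 1/7 = 85.7% for 7 days and 1 − 1/14 = 92.9% for 14 days. But the part of the second form's period that falls after the session starts does not depend on when the first form was completed. Take 20 minutes (second form straight after the two segments) to 60 minutes (30-minute session plus the 30-minute watch period, an assumed latest time):

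- 1 day: 20/1,440 = 1.4% to 60/1,440 = 4.2%
- 7 days: 20/10,080 = 0.2% to 60/10,080 = 0.6%
- 14 days: 20/20,160 = 0.1% to 60/20,160 = 0.3%

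So even then the second form would mostly rate time before the session. All these figures describe the period rated. They do not show how far patients' answers would move.

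**The case against.** The strongest objection is that the recall period comes from outside the document, and that it decides whether there is a problem at all, not only how large it is. That stands, and it is why the conclusion is conditional. It does not dispose of the point: as the plan is written, a reader cannot tell what period two of its endpoints refer to.

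Second, other measures might fill the gap. PGIC and heart rate do not, for the reasons given in the list of measures. The TRU-Pain questions might. So the correct statement is that no such rating is described, not that none is collected.

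Third, this is a feasibility pilot without a control group, and its effect size would be weak in any case. That is fair, and new items would not cure it: repeat testing and the wish to please would affect them too. But the plan goes beyond feasibility. It hypothesises symptom reduction, looks for significant change and uses the data for power.

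A reader might also infer that GAD-7 and PHQ-9 cannot move within one visit, so that their change is worthless and should be dropped as an endpoint. The document does not support that. It does not state the wording, and even under past-period wording present mood can colour what a patient recalls. Demoting two stated endpoints in favour of narrower single items would be a debatable trade.

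**Conclusion.** The point holds in conditional form. Established from the document: GAD-7 and PHQ-9 are repeated around one short session, apparently within a visit of about 90 minutes; their change is an endpoint, is examined for significance and feeds later power calculations; their recall wording is not stated; and no listed measure is described as a present-moment rating of anxiety or mood.

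Conditional on past-period wording of 1 day or more, and on a gap of about 20 to 90 minutes, at least 93.75% of the rated period is common to both completions (at least 99.1% for 7 days or longer). The change would then be an uncertain guide to the immediate effect and should not alone serve as an effect size. If the wording refers to the present moment, there is no problem.

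Feasibility is not affected. Nor is pain, provided the score asks about current pain; section 5 says only "current pain or baseline pain score >0", which does not settle it. Confidence is medium, because the recall wording and the TRU-Pain content are unknown. The change is worth making because it is cheap and answers the plan's own question more directly.

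**What to change.** 1. In section 4, add one anxiety item and one low-mood item, each asking about right now (for example on a 0–10 scale), immediately before and immediately after the session. If TRU-Pain items already ask this at both times, use those and say so.
2. In section 12, name these items as the measures of immediate change, and label them exploratory.
3. State the recall wording of GAD-7 and PHQ-9 at each completion, and what the TRU-Pain questions cover.
4. Keep GAD-7 and PHQ-9 change as planned. Unless the wording refers to the present moment, report it with a caution against using it alone to power later studies.

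Cost: 2 items × 2 times = 4 extra responses per patient, and 4 × 60 = 240 over the study, with no added visit, staff or procedure; none if suitable TRU-Pain items exist. Downsides: single items are narrower than the full scales, so low mood covers less than depressive symptoms. Two outcomes join a list with no named primary endpoint, hence the exploratory label. The lack of a control group remains.
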